**10.7. Appendix 7: Reporting Standards for Missing Data****10.7.1. Premature Withdrawals**

Element	Reporting Detail
General	
 
• Participant study completion (i.e. as specified in the protocol) was defined as those who completed all the study procedures, including a completion visit. .
 
• Withdrawn participants were not replaced in the study.
 
• All available data from participants who were withdrawn from the study will be listed and all available planned data will be included in summary tables and figures, unless otherwise specified.
 
• Withdrawal visits will be slotted as per Appendix 3: Assessment Windows or will be summarised as withdrawal visits.
 

**10.7.2. Handling of Missing Data**

Element	Reporting Detail
General	
 
• Missing data occurs when any requested data is not provided, leading to blank fields on the collection instrument: 
 
○ These data will be indicated by the use of a “blank” in participant listing displays. Unless all data for a specific visit are missing in which case the data is excluded from the table.
 
○ Answers such as “Not applicable” and “Not evaluable” are not considered to be missing data and should be displayed as such.
 
 
 

Responder of MAS	
 
• If MAS score is missing at the corresponding visit, the participant will be regarded as those who are a non-responder (i.e. non-responder imputation).
 

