## 3. PLANNED ANALYSES

### 3.1. Interim Analyses

The interim planned primary analyses will be performed after the completion of the following sequential steps:

1. All participants (except for early termination) complete the visit at Week 24 of the initial dose as defined in the protocol. The participants who complete that visit are defined as below.

The participant is re-treated at Week 12 visit in Blind Phase and completes the Week 12 visit in Open-label Phase.

The participant is re-treated at Week 16 visit in Blind Phase and completes the Week 12 visit in Open-label Phase.

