**CONFIDENTIAL**

207660

The participant is re-treated at Week 20 visit in Blind Phase and completes the Week 4 visit in Open-label Phase.

The participant completes the Week 24 visit in Blind Phase.

2. All required database cleaning activities have been completed and interim database release and database freeze has been declared by Data Management.
3. All criteria for unblinding the randomization codes have been met.
4. Randomization codes have been distributed according to RandAll NG procedures.
5. Interim analyses will be performed.

The interim analyses will be performed for regulatory submission. However subject level data will not be disclosed to people who work at the sites including investigators.

All planned interim analyses (i.e. Study population, Efficacy and Safety analyses) will be performed using data up to Week 24 visit for all participants.

For Rehabilitations, the data at Screening visit and Week 12 visit will be used for the interim analysis.

For Adverse Events, Liver Events and Medication, the data up to Week 24 visit is defined by using the start date. If the start date of these data is earlier than or same as the date of Week 24 visit defined above, these data will be included in the data up to Week 24 visit. Otherwise the data will not. See the decision tree ([Appendix 14](#)) to determine the Week 24 visit and date of the participant.

Cardiovascular Events will not be output in the interim analysis.

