**4. ANALYSIS POPULATIONS**

Population	Definition / Criteria	Analyses Evaluated
Screened	
 
Comprise of all screened participants
 
	
 
Study Population
 

Enrolled	
 
Comprise of all participants who meet the eligibility criteria at a screening and Day 1 visit.
 
	
 
Study Population
 

Intent-To-Treat 1 (ITT1)	
 
This population consists of all participants who are randomized in the study and who have at least 1 post-baseline efficacy assessment:
 
ITT is the primary efficacy analysis population, and the participants will be analyzed in line with the randomized treatment group
 
Any participant who receives a study treatment randomization number will be considered to have been randomized.
 
	
 
Study Population
 
Efficacy
 

ITT2	
 
This population consists of all participants in ITT1 population, who have at least 2 study treatments and who have at least 1 efficacy assessment after the 2nd treatment.
 
	
 
Study Population
 
Efficacy
 

ITT3	
 
This population consists of all participants in ITT2 population, who have at least 3 study treatments and who have at least 1 efficacy assessment after the 3rd treatment.
 
	
 
Study Population
 
Efficacy
 

ITT4	
 
This population consists of all participants in ITT3 population, who have 4 study treatments and who have at least 1 efficacy assessment after the 4th treatment.
 
	
 
Study Population
 
Efficacy
 

Safety1	
 
This population consists of all participants who are randomized in the study and who receive study treatment at least once
 
The participants will be analyzed based on the treatment actually given.
 
	
 
Safety
 

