**CONFIDENTIAL**

207660

Responder rate will be the proportion of the responder in the corresponding population, except for the participant of which joint was not evaluable. MAS score values in pronation of the forearm and shoulder flexors will be summarised using descriptive statistics, graphically presented and listed by visit and treatment cycle. Data up to Week 12 in each treatment cycle will be used for summary tables and Figures, whereas all data will be listed.

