**10.12.5. Efficacy Tables****10.12.5.1. Interim Analyses**

Efficacy: Tables					
No.	Population	IDSL / Example Shell	Title	Programming Notes	Deliverable
MAS					
2.01.	ITT1	EFF_T1	Summary of MAS score in Blind Phase	
 
Values and change from baseline
 
Summarize data up to Visit 5
 
	IA SAC
2.02.	ITT1	EFF_T2	Summary of the Results of Mixed Models for Repeated Measures of Change from Baseline in MAS scores in Blind Phase	Analyse data up to Visit 5	IA SAC
2.03.	ITT1	EFF_T3	Summary of Responder rate of MAS score at Week 6 in Blind Phase	Including subgroup analyses	IA SAC
2.04.	ITT1	EFF_T4	Summary of Responder rate of MAS score in Blind Phase	Summarize data up to Visit 5 Include Mantel Haenszel estimators	IA SAC
2.05.	ITT2	EFF_T1	Summary of MAS score in Open Label Phase (2nd Treatment)	
 
Values and change from baseline
 
Summarize data up to Visit 5
 
Three treatment arms (240, 400 and 240 + 400U)
 
	IA SAC
2.06.	ITT2	EFF_T5	Summary of Responder rate of MAS score in Open Label Phase (2nd Treatment)	
 
Summarize data up to Visit 5
 
Three treatment arms (240, 400 and 240 + 400U)
 
	IA SAC

CONFIDENTIAL

207660

Efficacy: Tables					
No.	Population	IDSL / Example Shell	Title	Programming Notes	Deliverable
DAS					
2.07.	ITT1	EFF_T1	Summary of Main Assessment Parameter and All Items of DAS in Blind Phase	
 
Values and change from baseline
 
Summarize data up to Visit 5
 
	IA SAC
2.08.	ITT1	EFF_T2	Summary of the Results of Mixed Models for Repeated Measures of Change from Baseline in Main Assessment Parameter of DAS in Blind Phase	Analyse data up to Visit 5	IA SAC
2.09.	ITT2	EFF_T1	Summary of Main Assessment Parameter and All Items of DAS in Open Label Phase (2nd Treatment)	
 
Values and change from baseline
 
Summarize data up to Visit 5
 
Three treatment arms (240, 400 and 240 + 400U)
 
	IA SAC
NRS for pain					
2.10.	ITT1	EFF_T1	Summary of NRS for pain in Blind Phase	
 
Values and change from baseline
 
Summarize data up to Visit 5
 
	IA SAC

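### Interim 2nd-treatment responder rates at open-label Weeks 6 and 12 keep Week-20 re-treaters in the denominator although their data stop at open-label Week 4

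*SAP*

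**What the plan says.** All references are to the amended SAP.

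- **Data cut (Section 3.1).** All interim analyses "will be performed using data up to Week 24 visit for all participants". What counts as that visit depends on when the participant was re-treated. For the Week-16 group: "The participant is re-treated at Week 16 visit in Blind Phase and completes the Week 12 visit in Open-label Phase". For the Week-20 group: "The participant is re-treated at Week 20 visit in Blind Phase and completes the Week 4 visit in Open-label Phase".
- **Population (Section 4).** ITT2 takes ITT1 participants with at least two treatments and "who have at least 1 efficacy assessment after the 2nd treatment".
- **Denominator (Section 7.3.1).** For the open-label cycles: "Responder rate will be the proportion of the responder in the corresponding population, except for the participant of which joint was not evaluable".
- **Missing scores (Section 10.7.2).** For responder status: "If MAS score is missing at the corresponding visit, the participant will be regarded as those who are a non-responder". The general entry of the same table reads: "Missing data occurs when any requested data is not provided, leading to blank fields on the collection instrument".
- **Displays (Sections 10.12.5.1 and 10.12.6.1).** Interim Table 2.06 and Figure 2.06 give the 2nd-treatment responder rate in ITT2 up to Visit 5, which is open-label Week 12, for 240, 400 and both groups pooled.
- **Purpose and status.** Section 3.1 says that the interim serves regulatory submission. Section 7.2.3 makes all open-label efficacy exploratory.

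**The concern.** A participant re-treated at Week 20 enters ITT2 through an open-label Week 2 or Week 4 assessment. The cut then removes that participant's Weeks 6 and 12. Nothing in Section 7.3.1 takes the participant out of the denominator at those visits, and Section 10.7.2 makes no exception for a visit that lies beyond the cut. The participant is counted as a failure whatever the actual response.

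The plotted responder rate would then step down between open-label Weeks 4 and 6 because follow-up was cut, and a reader could take this for waning of effect.

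The plan reasons differently elsewhere. Sections 7.1.4 and 7.2.4 present non-responder status as the strategy for early withdrawal, and an administrative cut is not a withdrawal. Section 7.3.7 censors time to retreatment at the last visit observed at the interim, so incomplete follow-up is recognised there.

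**Working it through.** The plan states no figure for this rate, so there is nothing to reproduce. The check has three parts.

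**1. Which visits are lost.** Study week = re-treatment week + open-label week, compared with the cut in Section 3.1.

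| Re-treated at | Wk 2 | Wk 4 | Wk 6 | Wk 12 | Cut (open-label) | Lost |
|---|---|---|---|---|---|---|
| Week 12 | 14 | 16 | 18 | 24 | Week 12 | none |
| Week 16 | 18 | 20 | 22 | 28 | Week 12 | none |
| Week 20 | 22 | 24 | 26 | 32 | Week 4 | Weeks 6 and 12 |

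Participants first re-treated at Week 24 have no post-retreatment assessment by the cut, so they are not in interim ITT2. Only the Week-20 group is affected, and only at open-label Weeks 6 and 12.

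**2. Form of the bias.** Let f be the share of interim ITT2 re-treated at Week 20 and p the responder rate, assumed the same whatever the time of re-treatment.

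- Rate under the written rules: (1 − f) × p + f × 0 = (1 − f)p
- Shortfall: p − (1 − f)p = f × p

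If late re-treaters respond at a different rate, the shortfall is f times their own rate.

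**3. Size.** The SAP gives neither f nor p. Assume that a proportion a qualifies at Week 12 and that, of those still waiting, a common proportion b qualifies at Week 16 and again at Week 20. Withdrawals are ignored.

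f = (1−a)(1−b)b ÷ [a + (1−a)b + (1−a)(1−b)b]

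- a = 0.5, b = 0.4: 0.12 ÷ (0.50 + 0.20 + 0.12) = 0.12/0.82 = 15%
- a = 0.6, b = 0.5: 0.10 ÷ (0.60 + 0.20 + 0.10) = 0.10/0.90 = 11%
- a = 0.3, b = 0.3: 0.147 ÷ (0.30 + 0.21 + 0.147) = 0.147/0.657 = 22%
- a = 0.6, b = 0.3: 0.084 ÷ (0.60 + 0.12 + 0.084) = 0.084/0.804 = 10.4%
- a = 0.3, b = 0.4: 0.168 ÷ (0.30 + 0.28 + 0.168) = 0.168/0.748 = 22.5%

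Over a = 0.3–0.6 and b = 0.3–0.5, f is about 10–23%. With an assumed true p of 75%, the reported rate is 0.75 × 0.90 = 67% down to 0.75 × 0.77 = 58%.

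The shortfall f × p for other values:

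| f | p = 0.5 | p = 0.9 |
|---|---|---|
| 0% | 0 points | 0 points |
| 5% | 2.5 points | 4.5 points |
| 10% | 5 points | 9 points |
| 20% | 10 points | 18 points |

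**The case against.** **A visit beyond the cut may not be missing at all.** The general entry in Section 10.7.2 describes missing data as requested data left blank, and a visit not yet due has not been requested. On that reading the imputation rule does not apply. This is a fair reading, and a reader who inferred that the plan expressly orders such visits to be scored as failures would go beyond the text. It does not rescue the rate, though. Section 7.3.1 still divides by the population less unevaluable joints, so these participants stay in the denominator without a response. A programmer might choose a smaller denominator, but the plan does not specify one.

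**Some material cannot be seen.** The decision tree in Appendix 14, which assigns each participant's cut-off, and the shell for Table 2.06 are not shown. The shell might already print per-visit counts, since Section 10.5.2 lists N, n, frequency and percentage for categorical data. That would help a reader to notice the problem, but it would not change the denominator in Section 7.3.1. For the Week-20 group, Section 3.1 already states the cut in words.

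**The consequence is limited.** This stands. Because the interim serves a submission, a reader might infer that the main efficacy result is affected. It is not: blind-phase responder rates stop at Week 12, before every cut. A reader might also infer a distorted comparison of 240 with 400 units. Unequal late re-treatment would bias the two columns unequally, but both groups receive 400 units in this uncontrolled phase, and no between-group test is planned. Final Table 2.27 and Figure 2.29 repeat the 2nd-treatment rates without the interim cut. At the interim itself, Table 2.05 gives MAS means for the same visits, with no imputation rule stated for them, which allows a cross-check.

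**Conclusion.** The point holds for one exploratory interim table and one figure. Read together, Sections 3.1, 4, 7.3.1 and 10.7.2 produce 2nd-treatment responder rates at open-label Weeks 6 and 12 that are too low by f × p whenever someone is re-treated at Week 20. If nobody is, the bias is zero.

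The direction follows from the text. The size does not: the drop from 75% to about 58–67% rests on assumed qualification proportions, an assumed response rate, and response unrelated to the time of re-treatment. The documents do not support calling the rates wrong by a known amount. Nor do they support extending the point to the blind-phase or final results. It is a modest defect, but worth closing because these figures belong to the package prepared for submission.

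**What to change.** In Sections 7.3.1 and 10.7.2, state that for interim open-label responder displays the denominator at each visit excludes ITT2 participants whose visit falls after their data cut-off. Keep non-responder imputation for withdrawals and for visits that were due but missed. Show the number not yet due at each visit in Table 2.06 and Figure 2.06.

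The work is a sentence in each section and a flag in the analysis dataset. The price is a smaller n at interim Weeks 6 and 12. Those two visits would also describe only participants re-treated at Weeks 12 and 16, so a footnote should say that the group differs from the one at Weeks 2 and 4.

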**10.7.2.1. Handling of Missing and Partial Dates**

Element	Reporting Detail
General	
 
• Partial dates will be displayed as captured in participant listing displays.
 

Concomitant Medications and Surgery	
 
• Partial dates for any concomitant medications recorded in the CRF will be imputed using the following convention: 
 
○ If the partial date is a start date, a '01' will be used for the day and 'Jan' will be used for the month
 
○ If the partial date is a stop date, a '28/29/30/31' will be used for the day (dependent on the month and year) and 'Dec' will be used for the month.
 
 
 
• The recorded partial date will be displayed in listings.
 

**10.8. Appendix 8: Values of Potential Clinical Importance**

This is not applicable to this study.

**10.9. Appendix 9: Population Pharmacokinetic (PopPK) Analyses**

This is not applicable to this study.

**10.10. Appendix 10: Pharmacokinetic / Pharmacodynamic Analyses**

This is not applicable to this study.

CONFIDENTIAL

207660

**10.11. Appendix 11: Abbreviations & Trade Marks****10.11.1. Abbreviations**

Abbreviation	Description
ADaM	Analysis Data Model
AE	Adverse Event
AIC	Akaike's Information Criteria
A&R	Analysis and Reporting
CDISC	Clinical Data Interchange Standards Consortium
CI	Confidence Interval
CPMS	Clinical Pharmacology Modelling & Simulation
CS	Clinical Statistics
CSR	Clinical Study Report
CTR	Clinical Trial Register
CV b / CV w	Coefficient of Variation (Between) / Coefficient of Variation (Within)
DBF	Database Freeze
DBR	Database Release
DOB	Date of Birth
DP	Decimal Places
eCRF	Electronic Case Record Form
EMA	European Medicines Agency
FDA	Food and Drug Administration
FDAAA	Food and Drug Administration Clinical Results Disclosure Requirements
GSK	GlaxoSmithKline
IA	Interim Analysis
ICH	International Conference on Harmonization
IDMC	Independent Data Monitoring Committee
IDSL	Integrated Data Standards Library
IMMS	International Modules Management System
IP	Investigational Product
ITT	Intent-To-Treat
MMRM	Mixed Model for Repeated Measures
PCI	Potential Clinical Importance
PD	Pharmacodynamic
PDMP	Protocol Deviation Management Plan
PK	Pharmacokinetic
PP	Per Protocol
PopPK	Population PK
QC	Quality Control
QTcF	Frederica's QT Interval Corrected for Heart Rate
QTcB	Bazett's QT Interval Corrected for Heart Rate
RAP	Reporting & Analysis Plan
RAMOS	Randomization & Medication Ordering System
SAC	Statistical Analysis Complete
SDSP	Study Data Standardization Plan

**CONFIDENTIAL**

207660

Abbreviation	Description
SDTM	Study Data Tabulation Model
SOP	Standard Operation Procedure
TA	Therapeutic Area
TFL	Tables, Figures & Listings

**10.11.2. Trademarks**

Trademarks of the GlaxoSmithKline Group of Companies
NONE

Trademarks not owned by the GlaxoSmithKline Group of Companies
SAS

CONFIDENTIAL

207660

**10.12. Appendix 12: List of Data Displays****10.12.1. Data Display Numbering**

The following numbering will be applied for RAP generated displays:

Section	Tables	Figures
Study Population	1.1 to 1.22	
Efficacy	2.1 to 2.53	2.1 to 2.55
Safety	3.1 to 3.138	3.1 to 3.2
Section	Listings	
ICH Listings	1 to 78	

**10.12.2. Mock Example Shell Referencing**

Non IDSL specifications will be referenced as indicated

Section	Figure	Table	Listing
Study Population		POP_Tn	POP_Ln
Efficacy	EFF_Fn	EFF_Tn	EFF_Ln
Safety	SAFE_Fn	SAFE_Tn	

**NOTES:**

- Non-Standard displays are indicated in the 'IDSL / Example Shell' or 'Programming Notes' column as '[Non-Standard] + Reference.'

**10.12.3. Deliverables**

Delivery	Description
IA SAC	Interim Analysis Statistical Analysis Complete
SAC	Final Statistical Analysis Complete

CONFIDENTIAL

207660

**10.12.4. Study Population Tables****10.12.4.1. Interim Analyses**

Study Population Tables					
No.	Population	IDSL / Example Shell	Title	Programming Notes	Deliverable
Participant Disposition					
1.01.	ITT1	ES1	Summary of Participant Disposition for the Participant Conclusion Record (Week 24)	ICH E3, FDAAA, EudraCT Participant disposition at Week 24. Include total arm (240 U + 400 U)	IA SAC
1.02.	Screened	ES6	Summary of Screening Status and Reasons for Screen Failure	Journal Requirements	IA SAC
1.03.	Enrolled	NS1	Summary of Number of Participant by Site ID	EudraCT/Clinical Operations	IA SAC
Protocol Deviation					
1.04.	ITT1	DV1	Summary of Important Protocol Deviations	ICH E3 Include total arm (240 U + 400 U)	IA SAC
Population Analysed					
1.05.	Screened	SP1	Summary of Study Populations	IDSL	IA SAC
Demographic and Baseline Characteristics					
1.06.	ITT1	DM1	Summary of Demographic Characteristics	ICH E3, FDAAA, EudraCT Include total arm (240 U + 400 U)	IA SAC
1.07.	Enrolled	DM11	Summary of Age Ranges	EudraCT	IA SAC
1.08.	ITT1	DM5	Summary of Race and Racial Combinations	ICH E3, FDA, FDAAA, EudraCT	IA SAC

CONFIDENTIAL

207660

Study Population Tables					
No.	Population	IDSL / Example Shell	Title	Programming Notes	Deliverable
1.09.	ITT1	POP_T1	Summary of Baseline Efficacy Parameters	
 
MAS scores in finger, thumb, wrist and elbow
 
Randomization Strata
 
Numeric Rating Scale for pain
 
Disability Assessment Scale
 
Include total arm (240 U + 400 U)
 
	IA SAC
Prior and Concomitant Medications					
1.10.	ITT1	CM1	Summary of Prior Medications	Include total arm (240 U + 400 U)	IA SAC
1.11.	ITT1	CM1	Summary of Concomitant Medications	ICH E3 Include total arm (240 U + 400 U)	IA SAC
1.12.	ITT1	POP_T2	Summary of Rehabilitation	Include total arm (240 U + 400 U)	IA SAC
1.13.	ITT1	SAFE_T4	Summary of Actual Dosage in Exposed Muscle Region by Treatment Cycle and Muscle Region.		IA SAC
1.14.	ITT1	SAFE_T4	Summary of Actual Dosage in Exposed Joint by Treatment Cycle and Joint		IA SAC

CONFIDENTIAL

207660

**10.12.4.2. Final Analyses**

Study Population Tables					
No.	Population	IDSL / Example Shell	Title	Programming Notes	Deliverable
Participant Disposition					
1.15.	ITT1	ES1	Summary of Participant Disposition for the Participant Conclusion Record	ICH E3, FDAAA, EudraCT Include total arm (240 U + 400 U)	SAC
Protocol Deviation					
1.16.	ITT1	DV1	Summary of Important Protocol Deviations	ICH E3 Include total arm (240 U + 400 U)	SAC
Population Analysed					
1.17.	Screened	SP1	Summary of Study Populations	IDSL	SAC
Prior and Concomitant Medications					
1.18.	ITT1	CM1	Summary of Prior Medications	Include total arm (240 U + 400 U)	SAC
1.19.	ITT1	CM1	Summary of Concomitant Medications	ICH E3 Include total arm (240 U + 400 U)	SAC
1.20.	ITT1	POP_T2	Summary of Rehabilitation	Include total arm (240 U + 400 U)	SAC
Actual dose					
1.21.	ITT1	SAFE_T4	Summary of Actual Dosage in Exposed Muscle Region by Treatment Cycle and Muscle Region.		SAC
1.22.	ITT1	SAFE_T4	Summary of Actual Dosage in Exposed Joint by Treatment Cycle and Joint		SAC

CONFIDENTIAL

207660

**10.12.5. Efficacy Tables****10.12.5.1. Interim Analyses**

Efficacy: Tables					
No.	Population	IDSL / Example Shell	Title	Programming Notes	Deliverable
MAS					
2.01.	ITT1	EFF_T1	Summary of MAS score in Blind Phase	
 
Values and change from baseline
 
Summarize data up to Visit 5
 
	IA SAC
2.02.	ITT1	EFF_T2	Summary of the Results of Mixed Models for Repeated Measures of Change from Baseline in MAS scores in Blind Phase	Analyse data up to Visit 5	IA SAC
2.03.	ITT1	EFF_T3	Summary of Responder rate of MAS score at Week 6 in Blind Phase	Including subgroup analyses	IA SAC
2.04.	ITT1	EFF_T4	Summary of Responder rate of MAS score in Blind Phase	Summarize data up to Visit 5 Include Mantel Haenszel estimators	IA SAC
2.05.	ITT2	EFF_T1	Summary of MAS score in Open Label Phase (2nd Treatment)	
 
Values and change from baseline
 
Summarize data up to Visit 5
 
Three treatment arms (240, 400 and 240 + 400U)
 
	IA SAC
2.06.	ITT2	EFF_T5	Summary of Responder rate of MAS score in Open Label Phase (2nd Treatment)	
 
Summarize data up to Visit 5
 
Three treatment arms (240, 400 and 240 + 400U)
 
	IA SAC

CONFIDENTIAL

207660

Efficacy: Tables					
No.	Population	IDSL / Example Shell	Title	Programming Notes	Deliverable
DAS					
2.07.	ITT1	EFF_T1	Summary of Main Assessment Parameter and All Items of DAS in Blind Phase	
 
Values and change from baseline
 
Summarize data up to Visit 5
 
	IA SAC
2.08.	ITT1	EFF_T2	Summary of the Results of Mixed Models for Repeated Measures of Change from Baseline in Main Assessment Parameter of DAS in Blind Phase	Analyse data up to Visit 5	IA SAC
2.09.	ITT2	EFF_T1	Summary of Main Assessment Parameter and All Items of DAS in Open Label Phase (2nd Treatment)	
 
Values and change from baseline
 
Summarize data up to Visit 5
 
Three treatment arms (240, 400 and 240 + 400U)
 
	IA SAC
NRS for pain					
2.10.	ITT1	EFF_T1	Summary of NRS for pain in Blind Phase	
 
Values and change from baseline
 
Summarize data up to Visit 5
 
	IA SAC
2.11.	ITT2	EFF_T1	Summary of NRS for pain in Open Label Phase (2nd Treatment)	
 
Values in each joint and change from baseline in only elbow.
 
Summarize data up to Visit 5
 
Three treatment arms (240, 400 and 240 + 400U)
 
	IA SAC

CONFIDENTIAL

207660

Efficacy: Tables					
No.	Population	IDSL / Example Shell	Title	Programming Notes	Deliverable
CGI of functional disability					
2.12.	ITT1	EFF_T1	Summary of CGI of functional disability by an investigator in Blind Phase	
 
Values only
 
Summarize data up to Visit 5
 
	IA SAC
2.13.	ITT2	EFF_T1	Summary of CGI of functional disability by an investigator in Open Label Phase (2nd Treatment)	
 
Values only
 
Summarize data up to Visit 5
 
Three treatment arms (240, 400 and 240 + 400U)
 
	IA SAC
2.14.	ITT1	EFF_T1	Summary of CGI of functional disability by a patient in Blind Phase	
 
Values only
 
Summarize data up to Visit 5
 
	IA SAC
2.15.	ITT2	EFF_T1	Summary of CGI of functional disability by a patient in Open Label Phase (2nd Treatment)	
 
Values only
 
Summarize data up to Visit 5
 
Three treatment arms (240, 400 and 240 + 400U)
 
	IA SAC
Patient-Reported Benefit of Injection					
2.16.	ITT1	EFF_T5	Summary of Patient-Reported Benefit of Injection in Blind Phase	
 
Summarize data up to Visit 5
 
	IA SAC
2.17.	ITT2	EFF_T5	Summary of Patient-Reported Benefit of Injection in Open Label Phase (2nd Treatment)	
 
Summarize data up to Visit 5
 
Three treatment arms (240, 400 and 240 + 400U)
 
	IA SAC
Time to Patient-Reported Onset of Spasticity Symptom Relief					
2.18.	ITT1	EFF_T6	Summary of Time to Patient-Reported Onset of Spasticity Symptom Relief		IA SAC
2.19.	ITT1	EFF_T7	Summary of Survival Analyses Results of Time to Patient-Reported Onset of Spasticity Symptom Relief in Blind Phase	
 
Survival function estimates will be summarized
 
	IA SAC

CONFIDENTIAL

207660

Efficacy: Tables					
No.	Population	IDSL / Example Shell	Title	Programming Notes	Deliverable
2.20.	ITT2	EFF_T7	Summary of Survival Analyses Results of Time to Patient-Reported Onset of Spasticity Symptom Relief in Open Label Phase (2nd Treatment)	
 
Survival function estimates will be summarized
 
Three treatment arms (240, 400 and 240 + 400U)
 
	IA SAC
Time to Qualification for Retreatment					
2.21.	ITT1	EFF_T8	Summary of Events in Which a Participant Meets the Criteria for Retreatment		IA SAC
2.22.	ITT1	EFF_T6	Summary of Time to Qualification for Retreatment		IA SAC
2.23.	ITT1	EFF_T7	Summary of Survival Analyses Results of Time to Qualification for Retreatment in Blind Phase	
 
Survival function estimates will be summarized
 
Two treatment arms (240 and 400U)
 
	IA SAC

